2 SCHEDULE OF ACTIVITIES

Table 2-1: Screening Procedural Outline (CA2097G8)–Not Applicable per Protocol Amendment 01

Procedure	Screening Visit	Notes ^a (All windows are based on calendar days)
Eligibility Assessments		
Informed Consent	X	Register in Interactive Response Technology (IRT) system to obtain participant number. Informed consent must be obtained prior to any study procedure, except for those done as part of routine clinical practice including, but not limited to, cystoscopy, urine cytology, transurethral resection of the bladder tumor (TURBT), or cross-sectional imaging. Study allows for re-enrollment of a participant who has discontinued participation as a pretreatment failure. If re-enrolled, the participant must be re-consented and assigned a new participant number from IRT.
Inclusion/Exclusion Criteria	X	Must be confirmed prior to randomization.
Medical History	X	All medical history relevant to the disease under study, which includes concomitant medications, prior cancer therapy, and American Joint Committee on Cancer stage. Also include smoking history (including electronic cigarettes) and alcohol history.
Tumor Sample Submission (Bladder Biopsy) ^b	X	Participants with CIS should have bladder mapping at baseline (see Section 9.1.5) by random biopsy or by fluorescence cystoscopy with biopsy of all areas of abnormality. If bladder mapping is not performed at baseline, this must be performed at Week 26 (\pm 5 week). For participants with clinical stage T1 disease, a repeat TURBT is required within approximately 8 weeks after the initial TURBT to confirm complete resection of disease and to ensure that no tumor has invaded the muscularis propria of the bladder prior to randomization.
Cystoscopy	X	See Section 9.1.3 .
Urine Cytology ^b	X	Sample will be reviewed by PRC prior to randomization. See Section 9.1.4 .
Body Imaging	X	Contrast enhanced computed tomography (CT) of the chest, contrast-enhanced CT/magnetic resonance imaging (MRI) of the abdomen and pelvis (including excretory imaging) and all other known/suspected sites of disease should be performed during screening within 90 days prior to randomization. Options for participants with contraindications to intravenous (IV) contrast are delineated in the protocol. See Section 9.1.7 .

Table 2-1: Screening Procedural Outline (CA2097G8)–Not Applicable per Protocol Amendment 01

Procedure	Screening Visit	Notes ^a (All windows are based on calendar days)
Other Imaging	X	As clinically indicated (see Section 9.1.7).
Biomarker Sampling		
Not applicable per Protocol Amendment 01.		
Safety Assessments		
Targeted Physical Examination, Measurements, Vital Signs and Performance Status	X	Height, weight, Eastern Cooperative Oncology Group (ECOG) Performance Status (PS) (Appendix 6), blood pressure, heart rate, and temperature must be collected within 14 days prior to randomization.
Electrocardiogram (ECG)	X	ECGs should be recorded after the participant has been supine for at least 5 minutes.
Assessment of Signs and Symptoms	X	Must be performed within 14 days prior to randomization.
Concomitant Medication Use	X	Must be collected within 14 days prior to randomization. Record vaccine use within 30 days prior to randomization.
Serious Adverse Event (SAE) Assessment	X	SAE collection from time of consent. All AEs (SAEs or non-serious AEs) associated with severe acute respiratory syndrome coronavirus 2 (SARS-CoV-2) infection collected from time of consent.
Laboratory Tests		
Complete Blood Count (CBC) with Differential, Chemistry, Endocrine, Viral, Urinalysis	X	All testing, except viral, must be performed within 14 days prior to randomization. Viral testing must be within 28 days prior to randomization. For human immunodeficiency virus (HIV): testing at sites where locally mandated; see Appendix 7 . Refer to Section 9.4.4 for list of laboratory tests to conduct.
Pregnancy Test (WOCBP Only)	X	Serum or urine pregnancy test (minimum sensitivity 25 IU/L or equivalent units of human chorionic gonadotropin [HCG]) to be done at screening visit and within 24 hours of first dose of study treatment.

^a Some of the assessments referred to in this section may not be captured as data in the case report form (CRF). They are intended to be used as safety monitoring by the treating physician. Additional testing or assessments may be performed as clinically necessary or where required by institutional or local regulations.

^b Complete instructions on collecting, processing, handling, and shipment of samples will be provided in a separate lab manual.

Table 2-2: On-treatment Procedural Outline for Arms A and B (CA2097G8)

Procedure ^a	Arm A: Nivolumab 480 mg IV Q4W Plus Intravesical BCG Arm B: Nivolumab-placebo IV Q4W Plus Intravesical BCG		
	Nivolumab/Nivolumab-placebo Visits^b Cycle 1 – Cycle 26 (Day 1 ± 3 days) (1 Cycle = 4 Weeks)	BCG Visits^{b,c} (± 3 days)	Notes ^d
Study Treatment			
Randomize	X	X	Participant will be randomized via IRT to Arm A or Arm B.
Dispense Study Drug	X	X	
First dose should be administered within 3 calendar days following randomization, but no earlier than ≥ 14 days following last TURBT/bladder biopsy.
 
Nivolumab/nivolumab-placebo will be administered at Day 1 of each cycle.
 
Bacillus Calumette-Guerin (BCG) will be administered as described in footnote “c.”

Safety Assessments			
Targeted Physical Examination, Measurements, Vital Signs, Performance Status	X		
For each cycle, weight, ECOG PS, blood pressure, heart rate, and temperature within 3 calendar days prior to dosing.
 
For Cycle 1 Day 1 and beyond, targeted physical examination to be performed only as clinically indicated.

Adverse Event (AE) Assessment (Including SAE)	Continuously		
Record at each visit. Collect continuously throughout the treatment period and for a minimum of 100 days following the last dose of study treatment.
 
All AEs (SAEs or non-serious AEs), including those associated with SARS-CoV-2 infection, must be collected continuously during the treatment period.
 
Participants will be followed for all SAEs and non-serious AEs of special interest (as defined in Section 9.2). All AEs (SAEs and non-serious AEs)

Table 2-2: On-treatment Procedural Outline for Arms A and B (CA2097G8)

Procedure ^a	Arm A: Nivolumab 480 mg IV Q4W Plus Intravesical BCG Arm B: Nivolumab-placebo IV Q4W Plus Intravesical BCG		
	Nivolumab/Nivolumab-placebo Visits^b Cycle 1 – Cycle 26 (Day 1 ± 3 days) (1 Cycle = 4 Weeks)	BCG Visits^{b,c} (± 3 days)	Notes ^d
			
associated with confirmed or suspected SARS-CoV-2 infection will be followed until:
 
 • Resolution • Condition stabilizes • Event is otherwise explained • Event is deemed irreversible • Participant is lost to follow-up (as defined in Section 8.3) • For suspected cases, until SARS-CoV-2 infection is ruled out 
See Section 9.2 for additional information on collection of AEs and SAEs.

Concomitant Medication Use	Continuously		Record at each visit.
Laboratory Tests			
CBC with Differential, Chemistry Panel Thyroid Testing	X		
Must be performed within 72 hours prior to nivolumab dosing. Refer to Section 9.4.4 for list of laboratory tests. Thyroid testing to be performed every 8 weeks (2 cycles).

Urinalysis		X	
Performed prior to dosing at visits BCG is administered. Microscopic analysis required for abnormal dipstick urinalysis or clinical symptoms suggestive of urinary tract infection. A urine culture should be sent if there is suspicion of a urinary tract infection.

Pregnancy Test (WOCBP Only)	X		Serum or urine within 24 hours prior to first dose and then every 4 weeks (± 1 week) regardless of dosing schedule.

Table 2-2: On-treatment Procedural Outline for Arms A and B (CA2097G8)

Procedure ^a	Arm A: Nivolumab 480 mg IV Q4W Plus Intravesical BCG Arm B: Nivolumab-placebo IV Q4W Plus Intravesical BCG				
	Nivolumab/Nivolumab-placebo Visits^b Cycle 1 – Cycle 26 (Day 1 ± 3 days) (1 Cycle = 4 Weeks)	BCG Visits^{b,c} (± 3 days)	Notes ^d		
Efficacy Assessments					
Not applicable per Protocol Amendment 01. Sites should continue efficacy assessments as per local standards of care.					
Imaging Assessments					
Body Imaging	See Notes	
Contrast-enhanced CT of the chest, contrast-enhanced CT/MRI of the abdomen and pelvis (including excretory imaging) and all other known/suspected sites of disease.
 
Imaging will be performed, per local standards of care, every 52 weeks (± 4 weeks) from randomization, as described in Section 9.1.7, or at the discretion of the investigator due to symptoms, to exclude disease progression, or to exclude UC in the upper urinary tracts.
			
Other Imaging		As clinically indicated (see Section 9.1.7).			
Health Outcomes					
Not applicable per Protocol Amendment 01.					
Biomarker Sampling					
Not applicable per Protocol Amendment 01.					
Pharmacokinetic (PK) and Immunogenicity					
Not applicable per Protocol Amendment 01.					

^a If a dose is delayed, the procedures scheduled for that same time point (except efficacy assessments) should also be delayed to coincide with when that time point's dosing actually occurs.

^b Where possible, BCG can be administered on the same visits as nivolumab/nivolumab-placebo and assessments for both study treatments can be combined.

^c Participants in the study will receive one induction course of BCG (6 doses - 1 dose weekly for 6 weeks) followed by maintenance BCG for a total of 3 years treatment. Maintenance dosing includes 3 doses of BCG at weekly intervals at months 3, 6, 12, 18, 24, 30, and 36 (see [Table 7.1.2-1](#) for dosing detail by week). BCG dose will be administered \pm 3 days of nivolumab/nivolumab-placebo dosing (with a minimum of 5 days between BCG doses). BCG treatment should not be given within 14 days after TURBT/bladder biopsy. Fourteen days is the minimum requirement; BCG can be delayed greater than 14 days after TURBT/bladder biopsy based on routine clinical practice. BCG administration is independent of nivolumab/nivolumab-placebo cycles and study visits, however, where possible, BCG can be administered on the same visits as nivolumab/nivolumab-placebo, in which case assessments for both study treatments can be combined.

^d Some of the assessments referred to in this section may not be captured as data in the CRF. They are intended to be used as safety monitoring by the treating physician. Additional testing or assessments may be performed as clinically necessary or where required by institutional or local regulations.

Table 2-3: Follow-up Procedural Outline (CA2097G8)

Procedure	Follow-up ^a (FU) Visits 1 and 2	Not applicable per Protocol Amendment 01 Survival Follow-up ^b	Not applicable per Protocol Amendment 01 Efficacy Follow-up	Notes ^c
Safety Assessments				
Targeted Physical Examination, Measurements, Vital Signs, and Performance Status	See note			Weight, ECOG PS, blood pressure, heart rate, and temperature, to be performed only as clinically indicated.
Adverse Events Assessment (Including Serious Adverse Events)	X	See Notes	See Notes	
Record at each visit.
 
All SAEs and non-serious AEs should be collected continuously during the treatment period and for a minimum of 100 days following discontinuation of study treatment.
 
Participants will be followed for all SAEs, non-serious AEs of special interest (as defined in Section 9.2), and all AEs (SAEs and non-serious AEs) associated with confirmed or suspected SARS-CoV-2 infection until:
 
 • Resolution • Condition stabilizes • Event is otherwise explained • Event is deemed irreversible

Table 2-3: Follow-up Procedural Outline (CA2097G8)

Procedure	Follow-up ^a (FU) Visits 1 and 2	Not applicable per Protocol Amendment 01 Survival Follow-up^b	Not applicable per Protocol Amendment 01 Efficacy Follow-up	Notes ^c
				
 Participant is lost to follow-up (as defined in Section 8.3) For suspected cases, until SARS-CoV-2 infection is ruled-out 
See Section 9.2 for additional information on collection of AEs and SAEs.

Concomitant Medication Assessment	X			Record at each visit.
Subsequent Bladder Cancer Treatment and Disease Assessment	X	X		To include cystectomy, radiotherapy, systemic chemotherapy, and progression.
Survival Status	X	X		Every 3 months after FU visit 2; may be accomplished by site visit or phone contact.
Laboratory Tests				
CBC with Differential, Chemistry Panel, Thyroid Testing	FU visit 1 - yes FU visit 2 - only if toxicities are present			Refer to Section 9.4.4 for full list of laboratory tests.

Table 2-3: Follow-up Procedural Outline (CA2097G8)

Procedure	Follow-up ^a (FU) Visits 1 and 2	Not applicable per Protocol Amendment 01 Survival Follow-up ^b	Not applicable per Protocol Amendment 01 Efficacy Follow-up	Notes ^c
Pregnancy (WOCBP Only)	X	See Notes	See Notes	Serum or urine pregnancy testing is only required at FU visit 1 and 2, unless increased frequency and duration is required per local regulations.
Imaging Assessments				
Not applicable per Protocol Amendment 01. Sites should continue imaging assessments as per local standards of care.				
Efficacy Assessments				
Not applicable per Protocol Amendment 01. Sites should continue efficacy assessments as per local standards of care.				
Health Outcomes				
Not applicable per Protocol Amendment 01.				
PK and Immunogenicity Assessments				
Not applicable per Protocol Amendment 01.				

^a FU visit 1 should occur 30 days from the last dose (\pm 7 days) of the last dose of study treatment or can be performed on the date of discontinuation if that date is greater than 42 days from the last dose. FU visit 2 occurs approximately 100 days (\pm 7 days) from last dose of study treatment. See [Section 5.1.3](#). Both follow-up visits should be conducted in person.

^b Not applicable per Protocol Amendment 01. Survival follow-up visits to occur every 3 months (\pm 14 days) from FU visit 2. Survival visit may be conducted in person or by telephone. Survival follow-up visits may coincide with efficacy follow-up visits (see below). BMS may request that survival data be collected on all treated participants outside of the 3-month specified window. At the time of such request, each participant will be contacted to determine their survival status unless the participant has withdrawn consent for all contact.

^c Some of the assessments referred to in this section may not be captured as data in the CRF. They are intended to be used as safety monitoring by the treating physician. Additional testing or assessments may be performed as clinically necessary or where required by institutional or local regulations.

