5.1.3 Follow-up Phase

The follow-up phase will begin when the decision to discontinue a participant from the last study treatment is made (no further study treatment) or when 3 years of study treatment has been completed (eg, a participant may be discontinued from nivolumab/nivolumab-placebo study treatment on or before 24 months but remains on maintenance BCG study treatment for 36 months [see [Sections 5.4.4](#) and [5.4.5](#)]).

Participants must be followed for at least 100 days after last dose of last study treatment.

- Follow-up (FU) visit 1 should occur 30 days from the last dose (± 7) days or can be performed on the date of discontinuation if that date is greater than 42 days from the last dose.
- FU visit 2 occurs approximately 100 days (± 7 days) from last dose of study treatment.
- Both visits should be conducted in person.

Not applicable per Protocol Amendment 01:

Survival follow-up begins after FU visit 2.

- Survival follow-up visits occur every 3 months (± 14 days) until the end of the study.

Not applicable per Protocol Amendment 01:

Efficacy follow-up:

- Efficacy assessments occur until disease recurrence (other than low-grade Ta) or progression, per PRC (based on a positive urinary cytology, bladder biopsy, or imaging), or treatment discontinuation, whichever is later.
- For participants who have not had PRC confirmed progression or recurrence during the on-treatment period, efficacy assessments will continue as per [Table 2-3](#) and [Section 9.1.8](#).
- Where scheduling allows, efficacy follow up and survival follow up can coincide.

Treatment beyond disease recurrence/progression is not permitted except in the case of a low-grade papillary Ta tumor (TaLG) UC recurrence only, or for participants with CIS and/or Ta at Week 13 (see [Section 8.1.4](#)).

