7.1.2 BCG Dosing

Participants should begin study treatment within 3 calendar days of randomization but no earlier than \geq 14 days following last TURBT/bladder biopsy. BCG and nivolumab/nivolumab-placebo should begin concurrently or within 3 days of each other. Cycle 1 will begin at the time of the first dose of study treatment.

Participants should receive an intravesical instillation of BCG weekly for 6 weeks starting on Day 1 of BCG treatment (induction period) and then weekly for 3 weeks at 3, 6, 12, 18, 24, 30 and 36 months after the first BCG dose (maintenance period) (see Table 7.1.2-1).

Table 7.1.2-1: Timing of Intravesical BCG Maintenance Dose

Time		Weekly BCG Dose (Days) ^a for 3 Weeks
Months	Week (Wk)	Days to Dose
3	13	Wk 14 (D1), Wk 15 (D1), Wk 16 (D1)
6	26	Wk 27 (D1), Wk 28 (D1), Wk 29 (D1)
12	52	Wk 53 (D1), Wk 54 (D1), Wk 55 (D1)
18	78	Wk 79 (D1), Wk 80 (D1), Wk 81 (D1)
24	104	Wk 105 (D1), Wk 106 (D1), Wk 107 (D1)
30	130	Wk 131 (D1), Wk 132 (D1), Wk 133 (D1)
36	156	Wk 157 (D1), Wk 158 (D1), Wk 159 (D1) ^b

^a Must be a minimum of 5 days between BCG doses.

^b Treatment will complete after 3 years and 15 days (\pm 3 days).

The BCG dose should be prepared and administered according to the package insert. **BCG may be obtained by the investigational sites, where possible/allowed by local regulations, as local commercial product in certain countries. These products should be prepared/stored/administered in accordance with the package insert or SmPC and local practice.**

Typical procedure is as follows:

- A urethral catheter will be inserted into the bladder by a qualified medical professional under aseptic conditions. The bladder will then be drained, after which the BCG suspension will be instilled slowly, under gravity. The catheter will then be withdrawn. BCG should not be given if the urethra is traumatized during catheter insertion or if there is gross hematuria.
- The participant should retain the BCG suspension for as long as possible for up to 2 hours. The participant should lie prone during the first 15 minutes following instillation, after which the participant is allowed to be in the upright position. At the end of 2 hours, the participant should void in the seated position. The participant will be instructed to maintain adequate fluid intake in the hours following BCG treatment to flush the bladder.

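### For a participant who completes nivolumab/placebo and stays on BCG, the routine post-treatment blood panel is postponed by up to about 14 months

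*Combined protocol and SAP*

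**What the plan says.** The relevant text is all in force under Protocol Amendment 01.

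- **On treatment (Table 2-2).** CBC, chemistry and thyroid tests are marked in the nivolumab/placebo column only: "Must be performed within 72 hours prior to nivolumab dosing". Thyroid tests are due every second cycle. At BCG visits the laboratory test marked is urinalysis: "Performed prior to dosing at visits BCG is administered". Pregnancy tests, where applicable, run on their own four-weekly schedule. Adverse events "must be collected continuously during the treatment period".
- **Follow-up (Table 2-3).** The blood panel is listed as: "FU visit 1 - yes FU visit 2 - only if toxicities are present". On timing, footnote a says: "FU visit 1 should occur 30 days from the last dose", within 7 days either way, counting from the last dose of study treatment.
- **Which last dose (Section 5.1.3).** "Participants must be followed for at least 100 days after last dose of last study treatment". The section gives the case at issue as its own example: "a participant may be discontinued from nivolumab/nivolumab-placebo study treatment on or before 24 months but remains on maintenance BCG study treatment for 36 months".
- **End of BCG (Table 7.1.2-1, footnote b).** "Treatment will complete after 3 years and 15 days".
- **No other source of time points.** Section 9.4 refers all planned safety time points back to the Schedule of Activities. Sections 2 and 9 allow or recommend further tests when clinically indicated.

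**The concern.** Follow-up visit 1 is the only post-treatment blood panel that the plan requires whether or not the participant has symptoms. It is timed from whichever drug ends last. Nivolumab/placebo is planned to end about a year before BCG, so for a planned completer the panel no longer follows nivolumab at any useful distance.

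Two other parts of the protocol make this look like a gap. During a nivolumab/placebo dose delay, laboratory studies continue every 4 weeks (Section 7.4.4.1) or every 6 weeks (Section 8.1.1). A participant on delay is therefore tested, while one who has just finished the drug is not. Also, the contraception rule in Section 6.1 (criterion 3c) treats nivolumab exposure as lasting about five half-lives after the last dose.

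What is at stake is the detection of asymptomatic liver, thyroid, renal or haematologic abnormalities while that exposure persists. Table 7.4-1 acts on several such values (transaminases, bilirubin, creatinine) by laboratory threshold alone.

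**Working it through.** **1. Reproduce the plan's own end date.** Take Cycle 1 Day 1 as day 1, with BCG started the same day. Week w Day 1 is then day 7(w − 1) + 1. Week 159 gives 7 × 158 + 1 = 1107. The footnote's 3 years and 15 days gives 156 × 7 + 15 = 1107. The two agree.

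**2. Last nivolumab/placebo dose.** There are 26 cycles of 28 days (Table 2-2), so Cycle 26 Day 1 is 25 × 28 + 1 = day 701. The last on-treatment bloods are drawn in the 72 hours before it.

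**3. Next scheduled blood panel.** This is the last study dose plus 30 days.

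| Last study dose | Day | FU visit 1 | Days after day 701 |
|---|---|---|---|
| Cycle 26, all treatment stopped | 701 | 731 | 30 |
| BCG Week 107 | 743 | 773 | 72 |
| BCG Week 133 | 925 | 955 | 254 |
| BCG Week 159 | 1107 | 1137 | 436 |

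With the ±7-day window the last row is 429 to 443 days, about 14 months (436 / 30.44 = 14.3). The 72 and 254 can be longer, because FU visit 1 may be held on the discontinuation date if that is more than 42 days after the last dose. If thyroid tests fall on odd cycles (an assumption, since the starting cycle is not stated), the last one is at Cycle 25, day 24 × 28 + 1 = 673, and the thyroid interval is 1137 − 673 = 464 days.

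**4. What is scheduled in between.** There are nine BCG visits, at 28, 35, 42, 210, 217, 224, 392, 399 and 406 days after day 701. Each has urinalysis and AE recording.

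**5. Exposure.** Section 6.1 sets 5 months as 30 days plus about five half-lives, which leaves about 4 months. The Week 105 to 107 BCG visits, 28 to 42 days after day 701, fall inside it.

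**6. How many participants (illustration only).** Assume 35 randomized (5% of 700), 17.5 per arm, and the Table 10.1-1 hazards, which Amendment 01 marks as no longer applicable. Event-free share: S(t) = exp{−[3h₁ + (t − 3)h₂]}. At Week 105, t = 728 / 30.44 = 23.92 months.

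- Nivolumab: exp{−[3 × 0.0521 + 20.92 × 0.0231]} = 0.528, so 17.5 × 0.528 = 9.2.
- Control: exp{−[3 × 0.0744 + 20.92 × 0.0330]} = 0.401, so 17.5 × 0.401 = 7.0.
- Total 16.2. With the Section 10.1 dropout (10% by month 24), the factor 0.9^(23.92/24) = 0.900 gives 14.6.
- The same calculation at Week 159 (36.34 months) gives 11.6 before dropout and 9.9 after.

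**7. After the change.** The window of 30 ± 7 days from day 701 is days 724 to 738. It contains Week 105 (day 729) and Week 106 (day 736). From a day-729 draw to FU visit 1 is still 1137 − 729 = 408 days.

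**The case against.** The strongest reply is that this is a design choice. FU visit 1 is an end-of-study-treatment visit, and no section sets a 30-day check after nivolumab as such. The same table separates pregnancy tests from dosing but leaves bloods attached to it, which could be deliberate. AE recording is continuous, and clinically indicated tests should be done. Much of this stands, and it limits the point. It does not remove it: the plan requires the FU visit 1 panel without symptoms, and discretionary testing does not replace a required draw.

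A reader might infer several stronger things that the documents do not support:

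- **That the panel is lost.** It is postponed; the participant still has it after BCG.
- **That like participants are treated differently.** No planned completer stops both drugs together. Those with bloods at about day 731 have ended BCG early.
- **That nothing scheduled could find a silent abnormality.** Urinalysis at BCG visits covers protein, glucose and blood (Section 9.4.4), so it can show some renal or glycaemic problems. It does not replace liver, thyroid or haematology tests.
- **That BCG doses in Weeks 105 to 107 lack a blood result they would otherwise have.** Bloods are never scheduled to inform BCG, even during weekly induction.
- **That nivolumab toxicity goes unchecked.** An event requiring nivolumab/placebo discontinuation also stops BCG (Section 8.1.2), so those participants reach FU visit 1.
- **That the safety tables are biased.** Both arms follow the same schedule, and the analyses are descriptive.
- **That 35 randomized, or about 16 affected, is a ceiling.** Participants already in screening could still be randomized (Section 3.1.1). Those with CIS or TaHG at Week 13 count as events but may continue treatment to Week 26, and beyond it if disease does not persist or recur (Section 8.1.4). On the Section 10.1 rates that leaves out up to 17.5 × (0.20 + 0.145), about 6 of 35. In the other direction, an event-free participant may have stopped BCG.

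**Conclusion.** The gap is real, and it concerns patient monitoring only. For a participant who completes nivolumab/placebo and continues BCG, no routine blood panel is scheduled until 30 days after the last BCG dose, which is 436 days after Cycle 26 if BCG is completed. Measured against a participant whose treatment ends altogether at Cycle 26, the shortfall is one draw at about 30 days. The long interval is not itself a further deficit, because that participant also has no routine bloods after about day 731.

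The day counts follow from the schedule, assuming on-time dosing and a common start day. The number affected is small but not bounded by the documents; roughly 15 depends on the assumed 35 randomized and on superseded hazards and dropout. The documents give no figure for how often such a draw would find anything. The change is worth making because it is cheap.

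**What to change.** Add a footnote to Table 2-2 and a sentence to Section 5.1.3: when BCG continues after nivolumab/placebo ends, the FU visit 1 CBC, chemistry and thyroid panel is also done 30 (±7) days after the last nivolumab/placebo dose. Do it at the Week 105 or 106 BCG visit where that falls in the window, and otherwise as a local draw. Keep FU visits 1 and 2 after the last BCG dose as they are. No extra AE contact is needed.

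The cost is one routine blood sample per affected participant, with no extra visit for an on-schedule completer. If delays push the last nivolumab/placebo dose later, the Week 107 visit (day 743) can serve up to a last dose on day 743 − 23 = 720. After that, or after an early stop with no BCG visit in the window, a separate draw is needed. The change restores the check at about 30 days and leaves the later interval (408 days if BCG is completed) as it is. It needs IRB/IEC approval and, where applicable, health-authority approval (Appendix 2), so it is best bundled with another amendment.
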